## **List of Abbreviations and Definition of Terms**

AE	Adverse Event
AESI	Adverse Event of Special Interest
ATC	Anatomical Therapeutic Chemical
AUC	Area under the concentration-time curve
AUC 0-8	AUC from time zero (= dosing time) to 8 hours postdose
AUC 0-8 /Dose	Dose-normalized AUC 0-8
CCI	[REDACTED]
BMI	Body Mass Index
BOR	Best Overall Response
CI	Confidence Interval
CIPD	Clinically Important Protocol Deviation
C max	Maximum Observed Concentration
C max /Dose	Dose-normalized C max
C pre	Predose (trough) observed concentration
C pre /Dose	Dose-normalized C pre
CnDn	Cycle and Study Day, e.g., Cycle 1 Day 1 (C1D1), Cycle 2 Day 1 (C2D1)
CR	Complete Response
CRF	Case Report Form
CRO	Contract Research Organization
CSR	Clinical Study Report
CTMS	Clinical Trial Management System
CV%	Coefficient of Variation
DCR	Disease Control Rate
DLT	Dose Limiting Toxicity
ECG	Electrocardiogram
ECOG	Eastern Cooperative Oncology Group
GeoCV%	Geometric Coefficient of Variation
GeoMean	Geometric Mean
GBS	Global Biostatistics
IAP	Integrated Analysis Plan

---

ICH	International Conference on Harmonization
irAE	Immune-Related Adverse Event
CCI	[REDACTED]
LLN	Lower Limit of Normal
LLOQ	Lower limit of quantification of the assay
LPS	Lipopolysaccharide
Max	Maximum
MedDRA	Medical Dictionary for Regulatory Activities
Min	Minimum
N	Number of subjects
n	Number of non-missing values
NCI-CTCAE	National Cancer Institute – Common Terminology Criteria for Adverse Events
NR	No Result
PCSA	Potentially Clinically Significant Abnormalities
PD	Progressive Disease
Pd	Pharmacodynamics
PFS	Progression Free Survival
PK	Pharmacokinetics
PR	Partial Response
PT	Preferred Term
QTcF	QT interval with Frederica's correction
R acc (AUC 0-8 )	Accumulation factor to assess the increase in exposure via AUC 0-8 following multiple dosing
R acc (C max )	Accumulation factor to assess the increase in maximum concentration following multiple dosing
RECIST 1.1	Response Evaluation Criteria in Solid Tumors version 1.1
SAE	Serious Adverse Event
SAP	Statistical Analysis Plan
SD	Stable Disease
SDTM	Study Data Tabulation Model
SMC	Safety Monitoring Committee
SOC	System Organ Class

---

StDev	Standard Deviation
TEAE	Treatment Emergent Adverse Event
t max	Time to reach the maximum observed concentration
CCI	[REDACTED]
ULN	Upper Limit of Normal
ULOQ	Upper limit of quantification of the assay
WHO-DD	World Health Organization Drug Dictionary

### 3 Modification History

Unique Identifier for Version	Date of IAP Version	Author	Changes from the Previous Version
1.0	07 Feb 2019	PPD	N/A – First version

### 4 Purpose of the Integrated Analysis Plan

The purpose of this Integrated Analysis Plan (IAP), authored together by Biostatistics and Quantitative Pharmacology, is to document technical and detailed specifications for the final analysis of data collected for the M4112 monotherapy dose escalation phase of protocol MS201408-0005. Due to termination of the study prior to commencement of Part IB and Part IC, only analyses for Part IA are covered in this IAP. Results of the analyses described in this IAP may be included in the Clinical Study Report (CSR) or a separate report. Additionally, the planned analyses identified in this IAP may be included in regulatory submissions or future manuscripts. Any post-hoc, or unplanned analyses performed to provide results for inclusion in the CSR but not identified in this prospective IAP will be clearly identified in the CSR.

A separate Statistical Analysis Plan (SAP) has been created to document analyses prepared for Safety Monitoring Committee (SMC) meetings (Appendix 18.2). The IAP is based upon Section 8 (Statistics) of the study protocol and protocol amendments and is prepared in compliance with ICH E9.

## 5 Objectives and Endpoints

### 5.1 Part IA (Dose Escalation – M4112 as Single Agent)

	Objective	Endpoint	IAP Section
Primary Objective	

To determine safety and tolerability or, if observed, the MTD, and to define the RP2D of M4112 as single agent in subjects with solid tumors

	

DLTs in subjects receiving M4112 as single agent during the first 4 weeks (Day 1 to Day 28 of Cycle 1) of treatment

TEAEs and TRAEs according to NCI-CTCAE 4.03 (including deaths) in subjects receiving M4112 as single agent from start of treatment up to the last Safety Follow-up Visit

Treatment-emergent changes from baseline in clinical laboratory measures, vital signs, ECOG PS, and physical examination findings in subjects receiving M4112 as single agent up to the last Safety Follow-up Visit

	15.1 15.2, 15.3 15.4, 15.5, 15.7
Secondary Objectives	

To characterize the PK parameters of M4112 as single agent

	

Plasma PK parameters for M4112: <math>AUC_{0-8}</math>, <math>C_{max}</math>, <math>t_{max}</math>, <math>AUC_{0-8}/Dose</math>, <math>C_{max}/Dose</math> (Days 1 and 15 of Cycle 1); <math>R_{acc}(AUC_{0-8})</math> and <math>R_{acc}(C_{max})</math> (Day 15/Day 1 of Cycle 1); <math>C_{pre}</math>, and <math>C_{pre}/Dose</math> (Days 8 and 15 of Cycle 1 and Day 1 of Cycle 2)

	16.1.2
	

To assess QT prolongation potential by central tendency, outlier analysis and the slope of exposure-QTc analysis to evaluate preliminary clinical activity parameters using RECIST 1.1

	

Slope of concentration-QTc (cQTc) regression based on time-matched ECG readings (3 or more replicates) and PK samples during Cycle 1 at Day 1 and Day 15, central tendency and outlier analyses for absolute QTcF, and delta QTc

	15.6.1
	

To evaluate preliminary clinical activity parameters using RECIST 1.1

	

BOR, DCR, and PFS using RECIST 1.1, up to confirmed tumor progression

	14.1, 14.2
Exploratory Objectives	CCI		16.2 16.2

AUC = area under the concentration-time curve; AUC0-8 = AUC from time zero (= dosing time) to 8 hours postdose; AUC0-8/Dose = dose-normalized AUC0-8; BOR = best overall response; Cmax = maximum observed concentration; Cmax/Dose = dose-normalized Cmax; Cpre = predose (trough) observed concentration; Cpre/Dose = dose-normalized Cpre; DCR = disease control rate; DLT = dose limiting toxicity; PFS = progression free survival; PK = pharmacokinetic; Racc(AUC0-8) = accumulation factor to assess the increase in exposure via AUC0-8 following multiple dosing; Racc(Cmax) = accumulation factor to assess the increase in maximum concentration following multiple dosing; TEAE = treatment emergent adverse event; tmax = time to reach the maximum observed concentration.

## 6 Overview of Planned Analyses

The planned analyses have been impacted by the decision to terminate this study early, prior to commencement of Parts IB and IC. In addition to the SMC analyses (detailed in a separate SAP, finalized on 30 Jan 2018), only a single, abbreviated final analysis will be performed. This final analysis will occur only after the last subject has completed the treatment phase of the study, with all study data in-house, all data queries resolved, and the database locked.

A data review meeting will be held prior to database lock. In addition, no database can be locked until this IAP has been approved.

## 7 Changes to the Planned Analyses in the Clinical Study Protocol

As a result of the decision to terminate this study early, only the M4112 monotherapy treatment arm (Part IA) was completed; the combination arms of CCI [REDACTED] and CCI [REDACTED], as described in the protocol CCI [REDACTED] were never opened for enrollment.

The following protocol-specified analyses will not be completed:

- Duration of response (DOR) and time to tumor response
- Concentration-QTc slope analysis of time-matched, replicate ECGs and PK samples
  - Summary statistics and scatterplots will be produced instead of linear modeling (Section 15.6.1)

CCI [REDACTED]

The PK parameters specified for calculation in the protocol included Cmin (defined as minimum observed postdose [trough] concentration) and Cmin/Dose. These parameters have been revised/clarified to Cpre and Cpre/Dose, where Cpre is defined as the predose (trough) observed concentration and may not reflect the true value at the end of the dosing interval.

The Dose Escalation Analysis Set was renamed to “DLT Analysis Set”. The definition was updated for clarifications.

## 8

## Protocol Deviations and Analysis Sets

### 8.1 Definition of Protocol Deviations and Analysis Sets

Important protocol deviations are protocol deviations that might significantly affect the completeness, accuracy, and/or reliability of the study data or that might significantly affect a subject's rights, safety, or well-being. They are coded as "Critical" or "Major" in the Clinical Trial Management System (CTMS) if identified via monitoring; they may also be identified from the database by medical review or programmatically.

The subject-level important protocol deviations to be identified by programming for this study are defined in [Section 18.1](#).

The following types of deviations will be identified and confirmed prior to or at the Data Review Meeting at the latest:

- Deviations from the inclusion and exclusion criteria
- Deviations post inclusion
- Clinically important protocol deviations (CIPDs) are defined as deviations leading to the exclusion of a subject from an analysis set (refer to [Section 8.2](#))

Other events/factors related to PK, which include, but may not be limited to, events that could affect PK, will be evaluated on a case-by-case basis by the PK Scientist:

- Vomiting immediately following oral dosing
- Sample processing errors that may lead to inaccurate bioanalytical results
- Incomplete data (e.g. due to lost samples, insufficient sample volumes for assay)
- Inaccurate dosing, dose reductions, missed dose(s) just prior to a PK dose, or dosing errors

In case of a deviation or event that may affect PK data, collected PK data which is likely to be affected may be excluded from the study results after consultation and agreement with Sponsor or Sponsor representative.

In general, data will not be excluded from the PK Analysis Set because of large PK sampling time deviations (since actual elapsed times will be used for PK analysis) or inadequate fasting prior to or following a PK dose. Additionally, given the patient population involved, data will not be excluded for an inaccurate dosing interval prior to a PK dose (though the affected doses will be identified in a data listing), or for concomitant medication violations.

All important protocol deviations are documented in SDTM datasets whether identified through site monitoring, medical review, or programming.

Protocol deviations will be classified as CIPDs or not, and confirmed prior to or at the Data Review Meeting before database lock.

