**The following potential risks of M4112 are**

1. Gastrointestinal intolerance including ulceration, bleeding with anemia and inflammation of gastric mucosa.
2. Liver toxicity either due to liver hypertrophy or direct liver lesions.
3. QT/QTc prolongation.
4. Inhibition/autoinduction of CYP3A4.
5. irAEs/autoimmune disorders.

Gastro-intolerance including ulceration and inflammation of gastric mucosa is a potential risk for M4112. The symptoms of gastrointestinal intolerance (nausea, vomiting, and diarrhea etc.) will be closely monitored, reported, and investigated. Discontinuation/interruption of treatment will be recommended for higher grade (Grade  $\geq 3$ ) events.

Liver toxicity is the clinically significant potential risk and relates to findings in animal toxicity studies. Subjects must be screened for potential impaired liver function or liver disease prior to treatment with a detailed medical history and clinical examination. All subjects enrolled in the clinical study should be counseled for early recognition and reporting of drug-related liver disease, and should be closely monitored in case of increased liver function tests and bilirubin (see Section 6.2.3).

QT/QTc prolongation is another important potential risk for M4112. A detailed medical history and medical examination to rule out a pre-existing heart disease and history of QT/QTc prolongation must be conducted (see Section 5.3.2). Subject inclusion and exclusion criteria and withdrawal criteria will exclude subjects deemed to be at risk for increase of QT. Time-matched triplicate digital ECG will be collected at Screening and at multiple time points (predose and postdose [Cmax]) in Cycle 1 and subsequent follow-up ECGs through all cycles. In M4112 monotherapy cohorts only (Part IA only), replicate ECGs (Holter) will also be collected on Days 1 and 15 of Cycle 1 for exposure-QTc analysis. Treatment modification guidance is described in Section 6.2.3.

M4112 is a sensitive substrate to CYP3A4 and it cannot be excluded that it inhibits or induces CYP3A4 to a clinically relevant extent. Strong inhibitors or inducers of CYP3A4 and drugs with a narrow therapeutic index, which are predominantly metabolized by CYP3A4, should be discontinued 7 days prior to treatment and avoided during treatment.

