## 6.5.2 Prohibited Medicines

Prohibited medicines are indicated in the exclusion criteria (see Section [5.3.2](#)).

During the study, any other investigational drug, chemotherapy, extensive radiotherapy (involving  $\geq 30\%$  of bone marrow) or any other anticancer therapy (cytotoxics, biologics or other targeted therapy) are prohibited.

In vitro assessments indicate that M4112 is a sensitive substrate to CYP3A4 and cannot exclude that it can inhibit or induce CYP3A4 at a clinically relevant extent. Strong inhibitors or inducers of CYP3A4, and drugs with a narrow therapeutic index, which are predominantly metabolized by CYP3A4 should be discontinued 7 days prior to treatment and avoided during treatment. **CCI**  
[REDACTED] An

updated list of nonpermitted drugs can be accessed via the following link:

<http://www.fda.gov/Drugs/DevelopmentApprovalProcess/DevelopmentResources/DrugInteractionsLabeling/ucm093664>

Drugs known to have a high risk to prolong QTc as per label or Credible Meds web site (formerly AZCert) are prohibited. For antihistamines only drugs with high risk of QTc prolongation (in the label) or risk mentioned in the label are prohibited (Diphenhydramine is considered of low risk and can be used)

Corticosteroids and immunesuppressants given systemically at therapeutic doses are not permitted throughout treatment other than for treatment of immune-related adverse events and for endocrine replacement therapy (equivalent to  $< 10$  mg prednisone daily).

Concomitant use of warfarin or other Vitamin K antagonists is also prohibited.

The solubility of M4112 is pH dependent; therefore, co-administration of antacid drugs, H2-blocker and proton pump inhibitors (PPIs) are likely to decrease the absorption of M4112. H2-blockers or PPIs should be stopped 5 days prior to the first treatment, and avoided during the entire treatment period with IMP. Antacid drugs should not be taken 1 h before IMP administration until 2 h after IMP administration.

The following treatments must not be administered during the study:

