## Appendix II: Strong Inhibitors and Inducers of CYP3A4 or Substrates with a Narrow Therapeutic Range and Drugs Causing QTc Prolongation

**Table with Examples of Inhibitors or Inducers of CYP3A4 Enzymes or Substrates with a Narrow Therapeutic Range**

Strong Inhibitors
Boceprevir, clarithromycin, conivaptan, grapefruit juice, indinavir, itraconazole, ketoconazole, lopinavir/ritonavir, mibefradil, nefazodone, neflifavir, posaconazole, ritonavir, saquinavir, telaprevir, telithromycin, voriconazole
Strong Inducers
Avasimibe, carbamazepine, phenytoin, rifampin, St. John's wort
Substrates With a Narrow Therapeutic Range
Alfentanil, astemizole a , cisapride a , cyclosporine, dihydroergotamine, ergotamine, fentanyl, pimozide, quinidine, sirolimus, tacrolimus, terfenadine a

CYP = cytochrome P450.

a Withdrawn from the US and certain other markets because of safety reasons.

Note: This is not an exhaustive list. For an updated list, see Tables 5, 6, and 7 in the following link:  
<http://www.fda.gov/Drugs/DevelopmentApprovalProcess/DevelopmentResources/DrugInteractionsLabeling/ucm080499.htm>

Note: A strong inhibitor is defined as an inhibitor that increases the AUC of a substrate sensitive for that CYP  $\geq$  5-fold or decreases clearance by  $> 80\%$ , and a strong inducer decreases AUC of a substrate by  $\geq 80\%$ .

Note: CYP substrates with narrow therapeutic range refers to drugs whose exposure-response relationship indicates that small increases in their exposure levels by the concomitant use of CYP inhibitors may lead to serious safety concerns (eg, Torsades de pointes).

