## 8.2 Definition of Analysis Sets and Subgroups

The analysis sets of subjects whose data will be included in the analyses described in this IAP are defined in [Table 1](#).

**Table 1** Analysis Sets

Population	Description
Screening (SCR)	All subjects who sign informed consent.
DLT	All subjects who received at least one dose of study intervention and meet at least one of the following criteria: 

- Received at least 5 planned cumulative total daily doses of M4112 in the first cycle (first 28 days) or

- Experienced at least one DLT during the DLT period, regardless of the administered number of doses of study intervention/completion of the DLT period

Safety	The Safety Analysis Set will include all subjects who receive at least 1 dose of study treatment.
Concentration-QTc Analysis Set	The cQTc Analysis Set will include all subjects with at least baseline and one on treatment measurement of time-matched ECG and M4112 plasma concentration collected during the dose-escalation phase.
M4112 Pharmacokinetic	All subjects from the Safety Analysis Set without clinically important protocol deviations/violations or events that would affect PK (see Section 8.1 ). Subjects in the PK Analysis Set must have received at least 1 dose of M4112 and must have sufficient M4112 plasma concentration data to enable the calculation of at least 1 PK parameter. Sufficient concentration data is defined as at least 3 valid, postdose concentration points in the PK profile to obtain any PK parameter.
Pharmacodynamics	All subjects who received at least 1 dose of M4112 and provide the predose and at least 1 postdose sample for Pd assessment.

cQTc = concentration-QTc response; DLT = dose-limiting toxicities; ECG = electrocardiogram;

Pd = pharmacodynamics; PK = pharmacokinetic; QTc = corrected QT interval.

There are no subgroup analyses planned for this study.

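### The SAP bars excluding PK data for any concomitant-medication violation, against the protocol's PK Analysis Set, and plans no flag or with/without comparison for a drug the protocol calls a sensitive CYP3A4 substrate

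*SAP*

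**What the plan says.** SAP section 8.1 lists events that the PK Scientist reviews case by case (vomiting, sample errors, incomplete data, dosing errors). It allows affected PK data to be left out once the Sponsor agrees. It then takes some deviations out of that discretion. Citing the patient population, it rules out exclusion for a wrong dosing interval "prior to a PK dose (though the affected doses will be identified in a data listing), or for concomitant medication violations". The promised listing belongs to the dosing-interval cases only.

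SAP section 8.2, Table 1, defines the PK set as "All subjects from the Safety Analysis Set without clinically important protocol deviations/violations or events that would affect PK" and refers back to section 8.1. Protocol section 8.4, Table 13, has nearly the same definition with no such reference and no carve-out.

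On the pharmacology, Protocol section 6.5.2 says that "M4112 is a sensitive substrate to CYP3A4" and that "co-administration of antacid drugs, H2-blocker and proton pump inhibitors (PPIs) are likely to decrease the absorption of M4112". Appendix II defines a strong inhibitor as one that "increases the AUC of a substrate sensitive for that CYP" at least 5-fold, and a strong inducer as one that lowers a substrate's AUC by at least 80%.

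In its visible text, SAP section 7 (changes from the protocol) does not mention the carve-out. SAP Appendix 18.1 has PK checks for vomiting, sample processing and dosing errors, but none for interacting drugs taken on treatment.

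**The concern.** A prohibited strong CYP3A4 drug taken around a PK day is, on the protocol's own account, an event that would affect PK. The protocol's analysis set would remove that subject. The SAP would keep the data and take away the PK Scientist's option to judge the case.

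The retained values would also be hard to recognise. Sections 16.1.1 and 16.1.2 flag only values left out of the set, section 12 lists concomitant medication without linking it to PK profiles, and no with/without analysis is planned. With about three subjects per level, one interaction-driven value could be taken for nonlinearity, high variability or a property of M4112 itself. For example, an inducer started between Day 1 and Day 15 would lower that subject's accumulation ratio. That would look like autoinduction of CYP3A4, which Protocol section 3.4.2.1 names as a potential risk.

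**Working it through.** **Inputs from the documents**
- Strong inhibitor: AUC factor f at least 5, or clearance down by more than 80%. Strong inducer: f at most 0.2 (Protocol Appendix II).
- Default cohort of 3 (Protocol 5.1). Anticipated layout of four levels of 3 and two of 6, which gives 12 + 12 = 24 (Protocol 8.1).
- Doses 100, 200, 400, 600, 800 and 900 mg.
- Power model ln(PK) = α + β ln(dose), 90% CI, at least 3 values per level (SAP 16.1.2). Below 3, only n, Min and Max are shown.

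**Assumed:** between-subject CV of AUC 30% to 70%, because the documents give none.

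**1. The protocol's own equivalence.** AUC = F × Dose / CL. An 80% fall in clearance gives 1/(1 - 0.8) = 5-fold, which agrees with Appendix II.

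**2. Cohort geometric mean.** One affected subject among n multiplies it by f^(1/n).
- n = 3: 5^(1/3) = 1.71 and 0.2^(1/3) = 0.58.
- n = 6: 5^(1/6) = 1.31 and 0.2^(1/6) = 0.76.
- For other effect sizes with n = 3, 2-fold gives 1.26 and 10-fold gives 2.15.
- The arithmetic mean of three otherwise equal values moves by (5 + 1 + 1)/3 = 2.33.

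**3. Accumulation ratio.** If an inducer acts on Day 15 but not Day 1, that subject's ratio is multiplied by 0.2 and the geometric mean of three ratios by 0.58. An equal effect on both days cancels.

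**4. Power-model slope.** The shift is (ln d - mean ln d) × ln f / Sxx. For six levels of three, mean ln d = 5.963, Sxx = 11.10 and ln 5 = 1.609.
- 100 mg: (4.605 - 5.963) × 1.609 / 11.10 = -0.20.
- 400 mg: (5.991 - 5.963) × 1.609 / 11.10 = 0.00.
- 900 mg: (6.802 - 5.963) × 1.609 / 11.10 = +0.12.

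Over the 9-fold dose range these are errors of 9^0.197 = 1.54-fold and 9^0.122 = 1.31-fold. For comparison, the slope SE at an assumed log-SD of 0.5 is 0.5/√11.10 = 0.15. A strong inducer (0.2) reverses the signs. With 24 subjects (the two 6-subject levels taken to be 800 and 900 mg) the shifts run from -0.18 to +0.08. With four levels of three (100 to 600 mg) they run from -0.28 to +0.24.

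**5. Effect on the 90% CI.** This was simulated with 20,000 trials, true slope 1 and six levels of three. With one 5-fold value at 100 mg, the interval wrongly excludes 1 in 34% of trials (CV 30%) or 19% (CV 70%), against a nominal 10%. At 900 mg the rate stays at 9% to 11%, but the interval widens: at CV 30% its mean width goes from 0.30 to 0.50.

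**6. Cost of excluding instead.** Dropping one of three subjects leaves n = 2. The level then loses its geometric mean and leaves the power model. Losing a level from six of three multiplies the slope SE by 1.58 (100 mg), 1.00 (400 mg) or 1.14 (900 mg).

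**The case against.** Five counter-arguments deserve weight.

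- **The SAP is internally consistent.** Table 1 refers to section 8.1, so it can be read as taking in the carve-out. This stands: the conflict is mainly with the protocol's Table 13.
- **Much is already caught.** Check INCEXC01 flags breached eligibility criteria, which include strong CYP3A4 and pH-raising drugs at entry. Monitoring and medical review find other deviations, and individual profiles and scatter plots would show an outlier. This stands in part. The missing piece is an on-treatment check tied to PK values, and a visible outlier does not show its cause.
- **Violations should be rare.** Protocol 5.3.2 sets a 7-day washout for CYP3A4 drugs, and 5.5.1 provides for withdrawal if a prohibited drug becomes necessary. This lowers the frequency. However, withdrawal may first be discussed with the Sponsor or Medical Monitor, and it does not remove profiles already collected.
- **The size is a worst case.** Appendix II speaks of substrate AUC, whereas the SAP analyses AUC0-8, Cmax and predose values. A reader might take 1.71 as a floor for every PK result. The documents do not support that, because a single-dose partial AUC or Cmax need not change as much as total AUC.
- **Exclusion costs information.** This also stands, as step 6 shows.

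A reader might also infer that the clause distorted dose escalation or the recommended Phase II dose. The documents do not show this. PK for SMC decisions came under the separate SMC plan of 30 January 2018, whose PK set has no visible carve-out. The disputed sentence belongs to the single abbreviated final analysis after early termination, although SAP 5.1 still lists the recommended dose as an objective.

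**Conclusion.** The point holds as a conflict between SAP section 8.1 and the protocol's PK Analysis Set. It is not declared in SAP section 7, and no flag or sensitivity analysis makes up for it.

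The 1.71-fold and 0.58-fold shifts rest on a strong inhibitor or inducer acting fully on a PK day in one of three subjects. The slope shift depends on dose position and matters most at the lowest dose. The CI error rates also depend on the assumed CV. The number of violations is unknown and probably small.

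What is at risk is PK characterisation, a secondary endpoint, and an exploratory dose-proportionality analysis. All analyses are descriptive, so no confirmatory conclusion is affected. Nor does it follow that affected data must be excluded: neither blanket retention nor blanket exclusion suits cohorts this small.

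**What to change.** 1. In SAP section 8.1, delete the closing clause on concomitant medication. These cases then go to the existing case-by-case PK Scientist review, to be settled before or at the Data Review Meeting.
2. Add an on-treatment PK check to Appendix 18.1 for prohibited CYP3A4 and acid-reducing drugs, run against the concomitant-medication data.
3. Flag affected profiles and predose values in the PK listings.
4. Present geometric means, accumulation ratios and the power-model slope with and without the flagged values. If removal takes a level below three values, say so beside the result.
5. Before the check cites a stop time, reconcile the protocol. Section 5.3.2 (criterion 5c) gives at least 1 week for drugs that raise gastric pH. Section 6.5.2 gives 5 days for H2-blockers and PPIs, and restricts antacids only around dosing.

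The cost is a few sentences, one data check and a small amount of extra output. SAP section 6 requires approval of the plan before database lock, so the change belongs before that lock.
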